4.1 Effectiveness Endpoints

Primary Effectiveness Endpoint

The primary endpoint is distance VA with study lenses (dispensed power) at Day 4, collected for each eye in logMAR.

4.2 Effectiveness Hypotheses

Primary Effectiveness

The null and alternative hypotheses are formulated in terms of the predefined margin of 0.05 for noninferiority:

$$H_0: \mu_{(T)} - \mu_{(C)} \geq 0.05$$

$$H_a: \mu_{(T)} - \mu_{(C)} < 0.05$$

where $\mu_{(T)}$ and $\mu_{(C)}$ denote the mean distance VA at Day 4 for Cassini and DT1, respectively, on the logMAR scale.

4.3 Statistical Methods for Effectiveness Analyses

4.3.1 Primary Effectiveness Analysis

A mixed effects repeated measures model will be utilized to test these hypotheses. The model will include terms for lens, visit, lens by visit interaction, sequence, and habitual lens brand stratum (DT1, non-DT1). Within-subject correlation due to the contralateral design will also be accounted for in the model. Lens difference [REDACTED] and the corresponding one-sided 95% upper confidence limit will be computed at Day 4. Noninferiority in distance VA will be declared if the upper confidence limit is less than 0.05.

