Key inclusion criteria  (See Section 8.1 for a complete list of inclusion criteria)	

Successful wearer of spherical soft contact lenses of the same brand in both eyes for a minimum of 5 days per week and 10 hours per day during the past 3 months.

Manifest cylinder <math>\leq 0.75</math> D in each eye.

BCVA (with manifest refraction) better than or equal to 0.10 (logMAR) in each eye.

									
Key exclusion criteria  (See Section 8.2 for a complete list of exclusion criteria)	

Any use of topical ocular medications and artificial tear or rewetting drops that would require instillation during study participation.

Wearing habitual contact lenses in an extended wear modality (routinely sleeping in lenses for at least 1 night per week) over the last 3 months prior to enrollment.

Habitual monovision or multifocal contact lens wearers.

									
Data analysis and sample size justification	
Planned Data Analysis
 
[REDACTED]
 
[REDACTED]
 

Endpoint	Comparison	Statistical Method	

Primary			

Distance VA	[REDACTED] vs DT1 NI	Mixed effects repeated measures NI margin = 0.05 (logMAR)	

	Endpoint	Comparison	Statistical Method	Primary			Distance VA	[REDACTED] vs DT1 NI	Mixed effects repeated measures NI margin = 0.05 (logMAR)
Endpoint	Comparison	Statistical Method								
Primary										
Distance VA	[REDACTED] vs DT1 NI	Mixed effects repeated measures NI margin = 0.05 (logMAR)								

Sample Size Justification	
Sample size required to demonstrate NI (one-sided $\alpha=0.05$ ) for VA is 10 at 80% power, with assumed standard deviation (SD) of 0.0567 for paired difference.	
Associated materials	N/A

**Table 3-1** Schedule of Study Procedures and Assessments

Procedure / Assessment	Visit 1 Screening / Baseline / Dispense	Visit 2 Day 4 Follow- up / Exit	Early Exit	Unscheduled Visit
	Day 1	Day 4 (-1/+1 Day)	N/A	N/A
Informed Consent	X			
Demographics	X			
Medical History	X	X	X	X
Concomitant Medications	X	X	X	X
Inclusion/Exclusion	X			
Habitual lens (brand, power)	X			
VA with habitual correction (OD, OS, Snellen distance)	X	X	X	(X)
Keratometry	X			
Manifest refraction	X	(X)	(X)	(X)

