## **8 STUDY POPULATION**

The study population consists of male and female subjects ages 18 and older with normal eyes (other than the need for optical correction for myopia) and who are successful spherical soft contact lens wearers in both eyes for a minimum of 5 days per week and 10 hours per day during the past 3 months. The eligible study population will be representative of the investigational product target population.

The aim is to enroll (consent) approximately 110 subjects at approximately 7 sites in the US, with 14 (intended minimum) to 16 (intended maximum) subjects per site, and a target of 100 total subjects completed. Site-specific targets may vary based upon individual site capabilities. [REDACTED]  
[REDACTED]  
[REDACTED]  
[REDACTED]

Estimated time needed to recruit subjects for the study is approximately 3 weeks; however, unanticipated circumstances may shorten or lengthen this time and would not require amendment of this protocol. Because a 5% screening failure rate is expected, approximately 110 subjects are targeted to be enrolled (consented).

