## 8.1 Inclusion Criteria

Written informed consent must be obtained before any study specific assessment is performed. Upon signing informed consent, the subject is considered enrolled in the study.

Subjects eligible for inclusion in this study must fulfill **all** of the following criteria:

1. Subject must be at least 18 years of age.
2. Subject must be able to understand and sign an IRB/IEC approved Informed Consent form.
3. Subject must be a successful wearer of spherical soft contact lenses of the same brand in both eyes for a minimum of 5 days per week and 10 hours per day during the past 3 months.
4. Manifest cylinder  $\leq 0.75$  D in each eye.
5. BCVA (with manifest refraction) better than or equal to 0.10 (logMAR) in each eye.
6. Subject must be able to wear contact lenses within a range of sphere power from -1.00 to -6.00 D (0.25 D steps).
7. Subject must possess spectacles and be willing to wear habitual spectacles for vision correction when study lenses are not worn, as needed for the duration of study participation.
8. Subject must be willing and able to wear the study lenses every day for at least 10 hours per day for the full duration of the study.
9. Subject must be willing to stop wearing habitual contact lenses for the duration of study participation, and wear only the study lenses provided by the site/Sponsor.
10. Differences in sphere power between the subjects' eyes (OD vs OS) must be  $\leq 2.5$  D.

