**Table 9–1**

**Test Product**

Test Product	[REDACTED] spherical soft contact lenses [REDACTED] LID220365)
Manufacturer	Alcon Laboratories, Inc. [name] USA
Indication for use and intended purpose in the current study	The investigational daily disposable contact lenses are indicated for the optical correction of refractive ametropia (myopia and hyperopia) in phakic and aphakic persons with nondiseased eyes with up to approximately 1.5 D of astigmatism that does not interfere with VA.
Product description and parameters available for this study	

• Material: delefilcon A

• Water content: 33%

• Power range: -1.00 to -6.00 D, 0.25 D steps

• Base curve (mm): 8.5

• Diameter (mm): 14.1

Formulation	Please refer to IB.
Usage	

• Wear:

○ Daily Wear

○ Contralateral

• Replacement period: Daily Disposable

	

• Exposure: daily for approximately 4 days total duration

• Lens Care: N/A

Number/Amount of product to be provided to the subject	Subject will be dispensed study lenses at Visit 1. Spare lens(es) will be provided to the subject.
Packaging description	Blister foil pack
Labeling description	
Lens Foil label includes:
 

- material name and identifier

- base curve

- diameter

- packing solution

- power

- lot number

- expiration date

- content statement

- investigational device statement

- sponsor information

- country of origin

 
• Provided in packages of approximately 40 lenses per power, identified with the following at a min:
 

- a color coded label stating the protocol number

- material identifier

- power

- an investigational use only statement

- tracking number

Training and/or experience requirements for device	No additional training or experience is required to administer the test product.
Storage conditions	Lenses should be stored at room temperature.

Supply	Alcon will provide test lenses. Refer to the MOP for a detailed description.
--------	---

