## 9.3 Treatment Assignment / Randomization

Qualifying subjects will be randomized in a 1:1 ratio to receive treatment (lenses) in a contralateral sequence.

Sequence	EDC/randomization integration system	
Sequence 1	LID220365(OD)/LID006961(OS)	
Sequence 2	LID006961(OD)/LID220365(OS)	

Only after signing the ICF, a subject will be assigned a subject number by the electronic data capture system.

[figure not shown]
A randomization list will be generated using a validated system that automates the random assignment of treatment (lens sequence) to randomization numbers in the specified ratio. Subjects will be assigned treatment (lens sequence) according to the randomization list uploaded in the EDC/randomization integration system. The randomization list will be generated and maintained by the study sponsor.

At Visit 1, all eligible subjects will be randomized via the EDC/randomization integration system to one of the treatments (lens sequences). The investigator or delegate will access the respective system after confirming that the subject meets all the eligibility criteria. A randomization number will be automatically assigned to the subject according to the subject randomization list but will not be communicated to the site user. The EDC/randomization integration system will inform the site user of the treatment (lens sequence) assignment to be dispensed to the subject.

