#### 12.4.1.2 Analysis Methods

A mixed effects repeated measures model will be utilized to test these hypotheses. The model will include terms for lens, visit, lens by visit interaction, sequence, and habitual lens brand

(DT1, non-DT1). Within-subject correlation due to the contralateral design will also be accounted for in the model. Lens difference [REDACTED] and the corresponding one-sided 95% upper confidence limit will be computed at Day 4. Noninferiority in distance VA will be declared if the upper confidence limit is less than 0.05.

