10 APPENDIX

Table 10-1 Schedule of Study Procedures and Assessments

Procedure / Assessment	Visit 1 Screening / Baseline / Dispense	Visit 2 Day 4 Follow- up / Exit■	Early Exit	Unscheduled Visit
	Day 1	Day 4 (-1/+1 Day)	N/A	N/A
Informed Consent	X			
Demographics	X			
Medical History	X	X	X	X
Concomitant Medications	X	X	X	X
Inclusion/Exclusion	X			
Habitual lens (brand, power■)	X			
VA with habitual correction (OD, OS, Snellen distance)■	X	X	X	(X)
Keratometry	X			
Manifest refraction	X	(X)	(X)	(X)
BCVA with manifest refraction (OD, OS, logMAR distance)	X	(X)	(X)	(X)

Procedure / Assessment	Visit 1 Screening / Baseline / Dispense	Visit 2 Day 4 Follow- up / Exit■	Early Exit	Unscheduled Visit
	Day 1	Day 4 (-1/+1 Day)	N/A	N/A
Biomicroscopy	X	X	X	(X)
Determine and record study lenses power (dispensed power, OD, OS)	X			
VA with study lenses (dispensed power)■ (OD, OS, logMAR distance)	X	X	(X)	(X)

Procedure / Assessment	Visit 1 Screening / Baseline / Dispense	Visit 2 Day 4 Follow- up / Exit■	Early Exit	Unscheduled Visit
	Day 1	Day 4 (-1/+1 Day)	N/A	N/A
Unplanned lens replacement with reason		(X)		(X)
AEs	X	X	X	X
Device deficiencies	X	X	X	X

Procedure / Assessment	Visit 1 Screening / Baseline / Dispense	Visit 2 Day 4 Follow- up / Exit	Early Exit	Unscheduled Visit
	Day 1	Day 4 (-1/+1 Day)	N/A	N/A
Exit Form	(X)	X	X	(X)

(X) Assessment performed as necessary, e.g., decrease of VA by 2 lines or more with investigational product

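### The primary model leaves out per-eye Visit 1 logMAR BCVA, a cheap chance of a tighter lens contrast; validity and planned power are not affected

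*SAP*

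**What the plan says.** SAP 4.3.1 specifies a mixed effects repeated measures model: "The model will include terms for lens, visit, lens by visit interaction, sequence, and habitual lens brand stratum (DT1, non-DT1"). Protocol 12.4.1.2 agrees: "The model will include terms for lens, visit, lens by visit interaction, sequence, and habitual lens brand", again split into DT1 and non-DT1. Both allow for within-subject correlation and declare noninferiority if the one-sided 95% upper limit for the Day 4 lens difference is below 0.05 logMAR. No redaction interrupts either list of terms.

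Three acuity measures are visible at Visit 1 in Protocol Table 3-1 and SAP Table 10-1:

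- "BCVA with manifest refraction (OD, OS, logMAR distance"), required at Visit 1. It is also an entry criterion (Protocol 8.1): "BCVA (with manifest refraction) better than or equal to 0.10 (logMAR) in each eye".
- "VA with habitual correction (OD, OS, Snellen distance"), which is not on the logMAR scale.
- VA with study lenses in logMAR, which needs the assigned lenses and so follows randomization.

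Protocol 9.3 fixes the order of events: "The investigator or delegate will access the respective system after confirming that the subject meets all the eligibility criteria". BCVA is therefore known for each eye before the lens assignment is drawn.

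**The concern.** In a contralateral design the lens effect is estimated from the difference between a subject's two eyes. Sequence and habitual lens brand take one value per subject, so they cancel from that difference when both eyes are observed. Modelling the within-subject correlation removes what the two eyes share, not what separates them. If one eye can attain better acuity than the other, that gap stays as noise in the lens contrast. Visit 1 study-lens VA does not fill the place of a baseline: it enters as an outcome and, with complete data and a lens by visit term, does not by itself tighten the Day 4 contrast.

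An eye-level covariate measured before randomization could absorb part of that noise, and the trial already collects one. At stake is the width of the reported confidence limit, which is the trial's main quantitative result.

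**Working it through.** **Inputs from the documents.** SD of the paired difference 0.0567, from study CLX679-E001 (Protocol 3; SAP 7). Margin 0.05 logMAR, one-sided alpha 0.05. Required N of 10 at 80% power and 14 at 90% (SAP 7). Protocol 8 sets "a target of 100 total subjects completed".

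**Assumed.**
- True difference 0 for the plan's sample size, since the readable text gives none.
- 0.0567 applies to the between-eye test-minus-comparator (T−C) difference. The design of CLX679-E001 is not stated.
- rho, the correlation between the T−C difference in BCVA and the T−C difference in Day 4 study-lens VA, from 0 to 0.6.
- Complete data.

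**Step 1: the plan's own figure.** For a paired noninferiority t-test with noncentral t, power is 0.823 at N = 10. It first passes 90% at N = 13 (0.911); N = 14 gives 0.930. Rounding up to an even number for the two sequences gives 10 and 14, as stated.

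**Step 2: unadjusted model, N = 100.**
- SE = 0.0567/√100 = 0.00567.
- Half-width = t(0.95, 99) × SE = 1.6604 × 0.00567 = 0.0094.
- Largest observed difference that still passes = 0.05 − 0.0094 = 0.0406.

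**Step 3: adjusted model.** SE = 0.00567 × √(1 − rho²) × √(1 + 1/97), with t(0.95, 98) = 1.6606. The last factor, √(1 + 1/(N − 3)), is the cost of estimating the slope. Power uses noncentral t with the same SE, at a true difference of 0.03, which the plan does not posit.

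| Model | Change in SE | Half-width | Largest passing difference | Power at 0.03 |
|---|---|---|---|---|
| Unadjusted | – | 0.0094 | 0.0406 | 0.968 |
| rho 0 | +0.5% | 0.0095 | 0.0405 | 0.967 |
| rho 0.1 | 0.0% | 0.0094 | 0.0406 | 0.968 |
| rho 0.2 | −1.5% | 0.0093 | 0.0407 | 0.972 |
| rho 0.3 | −4.1% | 0.0090 | 0.0410 | 0.978 |
| rho 0.6 | −19.6% | 0.0076 | 0.0424 | 0.997 |

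Break-even: (1 − rho²)(1 + 1/97) = 1 gives rho = √(1/98) = 0.101. At a true difference of 0.02, power is above 0.999 in every row.

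**Step 4: validity.** Simulation under the null (true difference 0.05, N = 100, 20,000 runs) gave these rejection rates, unadjusted and adjusted: 0.051 and 0.052 when BCVA explains none of the paired variance, 0.053 and 0.051 when it explains 25%, and 0.048 and 0.048 when it explains 50%. Bias was below 0.0001 logMAR in both models.

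**Step 5: slope specification.** A two-visit simulation used 8,000 trials per cell, an assumed correlation of 0.5 between the Visit 1 and Day 4 differences, and unstructured covariance. If rho were 0.6 at Visit 1 but 0 at Day 4, a slope common to both visits would widen the Day 4 half-width from 0.0094 to 0.0104. Visit-specific slopes leave it at 0.0094. With equal rho at both visits, the two specifications agree to within 0.0001.

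**The case against.** The strongest case against raising this is that the plan is valid as written. Protocol and SAP agree on the model, the trial has ten times the subjects needed for 80% power, and a simple prespecified model is defensible. The benefit rests wholly on rho, and two features may keep rho small. The BCVA entry limit restricts how far the two eyes can differ. The endpoint is also measured through spherical lenses ("Power range: -1.00 to -6.00 D, 0.25 D steps"), which leave residual cylinder that BCVA with manifest refraction does not reflect. At rho 0.3 the passing threshold moves by only 0.0004 logMAR (0.0406 to 0.0410). The SD is a further weak point: if the pairs in CLX679-E001 were the same eye under two lenses, 0.0567 would contain no between-eye acuity component, the very part that adjustment would remove.

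All of this stands, and it limits the point to precision. It does not remove the point: the covariate is already collected, and with visit-specific slopes the worst case is about 0.5% in SE.

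A reader might infer more than the documents support:

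- **That the omission biases the test or inflates its error rate.** Which eye receives which lens is randomized, so the unadjusted contrast is unbiased and holds its level.
- **That the trial is short of power.** The stated sample size reproduces without any covariate.
- **That the gain is known to be material.** No passage supports a rho of 0.3 or 0.6.
- **That BCVA is used nowhere in the analysis.** Some sections are redacted, so only the primary model can be judged.

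**Conclusion.** The point holds as a cheap improvement in precision, worth considering; it is not an error in the plan. The primary model omits the one visible pre-randomization, eye-level acuity on the endpoint's scale, and none of its listed covariates can remove between-eye differences from the lens contrast. Across assumed rho of 0 to 0.6, the effect on the half-width runs from a loss of about 0.5% to a gain of about 20%, with no gain below about 0.10. The noninferiority conclusion is very unlikely to change; power differs visibly only for true differences nearer the margin than any the plan posits.

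These sizes rest on the assumed rho range, on complete data for 100 subjects, and on 0.0567 being the right SD for the between-eye difference. The half-widths scale in proportion to that SD.

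**What to change.** Before unmasking, add two covariates to the primary model in SAP 4.3.1: eye-level Visit 1 BCVA (logMAR) and the subject's two-eye mean BCVA. The mean lets the eye-level slope reflect differences between a subject's eyes rather than between subjects. State that the slopes are visit-specific, which avoids the loss in Step 5. Keep the present unadjusted model as a sensitivity analysis, and align Protocol 12.4.1.2.

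No new data are needed. The change adds four model terms with visit-specific slopes and costs the Day 4 contrast about one degree of freedom, with up to 0.5% in SE if rho is 0. The main cost is documentation. One route is a protocol amendment, which Protocol 4 sends to the IRB/IEC unless the change is only logistical or administrative, in a study expected to finish in about 4 weeks. The other, under Protocol 12, is a deviation detailed in the study report. If the sponsor judges that cost too high, the present model remains valid.

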4.6 Interim Analysis for Effectiveness

No interim analysis is planned [REDACTED]

5 Safety Analysis Strategy

The focus of the safety analysis will be a comprehensive descriptive assessment of occurrence of adverse events as well as the other listed parameters. Therefore, no inferential testing will be done for the safety analysis.

5.1 Safety Endpoints

The safety endpoints are:

- AEs
- Biomicroscopy findings
 - Limbal hyperemia
 - Bulbar hyperemia
 - Corneal staining
 - Conjunctival staining
 - Palpebral conjunctival observations
 - Corneal epithelial edema
 - Corneal stromal edema
 - Corneal vascularization
 - Conjunctival compression/indention
 - Chemosis
 - Corneal infiltrates
 - Other findings
- Device deficiencies

5.2 Safety Hypotheses

There are no formal safety hypotheses in this study. The focus of the safety analysis will be a comprehensive descriptive assessment of safety endpoints listed in Section 5.1.

5.3 Statistical Methods for Safety Analyses

The analysis set for all safety analyses is defined in Section 2.1. Baseline will be defined as the last measurement prior to exposure to study lenses. For Biomicroscopy data, baseline will be defined as Visit 1. Safety variables will be summarized descriptively.

5.3.1 Adverse Events

The applicable definition of an AE is in the study protocol. All AEs occurring from when a subject signs informed consent to the time of their study exit will be accounted for in the reporting.

Presentation of AEs will be separated into pre-treatment AEs and treatment-emergent AEs as defined below:

- Pre-treatment AE: an event that occurs after signing informed consent but prior to exposure to study lenses.
- Treatment-emergent: an event that occurs from first exposure to study lenses until the subject exists from the study.

The following tables and supportive listings will be provided:

- Incidence of All Ocular Treatment-Emergent Adverse Events
- Incidence of Ocular Serious Treatment-Emergent Adverse Events
- Incidence of Ocular Significant Nonserious Treatment-Emergent Adverse Events
- Incidence of All Nonocular Treatment-Emergent Adverse Events
- Incidence of Nonocular Serious Treatment-Emergent Adverse Events
- Listing of All Ocular Treatment-Emergent Adverse Events
- Listing of All Nonocular Treatment-Emergent Adverse Events
- Listing of All Ocular Pre-Treatment Adverse Events
- Listing of All Nonocular Pre-Treatment Adverse Events

5.3.2 Biomicroscopy Findings

The following tables and supportive listings will be provided:

- Frequency and Percentage for Biomicroscopy Findings by Visit
- Incidence of Increased Severity by 2 or More Grades in Biomicroscopy Findings
- Listing of Subjects With Other Biomicroscopy Findings
- Listing of Subjects With Conjunctival Compression/Indentation or Chemosis
- Listing of Subjects With Increased Severity by 2 or More Grades in Biomicroscopy Findings
- Listing of Subjects with Infiltrates

5.3.3 Device Deficiencies

The following tables and supportive listings will be provided:

- Frequency of Treatment-Emergent Device Deficiencies
- Listing of Treatment-Emergent Device Deficiencies
- Listing of Device Deficiencies Prior To Treatment Exposure

7 SAMPLE SIZE AND POWER CALCULATIONS

Sample size required to demonstrate NI (one-sided $\alpha=0.05$) for VA [REDACTED]

Endpoint	SD Paired Difference (CLX679-E001)	N		NI or EQV margin
		80% power	90% power	
Visual Acuity	0.0567 (Overall)	10	14	0.05 logMAR (NI)

9 REVISION HISTORY

This is the original (Version 1.0) Statistical Analysis Plan for this study. This version of the Statistical Analysis Plan is based on Version 1.0 of the study protocol.

10 APPENDIX

Table 10-1 Schedule of Study Procedures and Assessments

Procedure / Assessment	Visit 1 Screening / Baseline / Dispense	Visit 2 Day 4 Follow- up / Exit■	Early Exit	Unscheduled Visit
	Day 1	Day 4 (-1/+1 Day)	N/A	N/A
Informed Consent	X			
Demographics	X			
Medical History	X	X	X	X
Concomitant Medications	X	X	X	X
Inclusion/Exclusion	X			
Habitual lens (brand, power■)	X			
VA with habitual correction (OD, OS, Snellen distance)■	X	X	X	(X)
Keratometry	X			
Manifest refraction	X	(X)	(X)	(X)
BCVA with manifest refraction (OD, OS, logMAR distance)	X	(X)	(X)	(X)

Procedure / Assessment	Visit 1 Screening / Baseline / Dispense	Visit 2 Day 4 Follow- up / Exit■	Early Exit	Unscheduled Visit
	Day 1	Day 4 (-1/+1 Day)	N/A	N/A
Biomicroscopy	X	X	X	(X)
Determine and record study lenses power (dispensed power, OD, OS)	X			
VA with study lenses (dispensed power)■ (OD, OS, logMAR distance)	X	X	(X)	(X)

Procedure / Assessment	Visit 1 Screening / Baseline / Dispense	Visit 2 Day 4 Follow- up / Exit■	Early Exit	Unscheduled Visit
	Day 1	Day 4 (-1/+1 Day)	N/A	N/A
Unplanned lens replacement with reason		(X)		(X)
AEs	X	X	X	X
Device deficiencies	X	X	X	X

Procedure / Assessment	Visit 1 Screening / Baseline / Dispense	Visit 2 Day 4 Follow- up / Exit	Early Exit	Unscheduled Visit
	Day 1	Day 4 (-1/+1 Day)	N/A	N/A
Exit Form	(X)	X	X	(X)

(X) Assessment performed as necessary, e.g., decrease of VA by 2 lines or more with investigational product
